## **PART-D**

### **1. Introduction:**

Secondary hyperparathyroidism (SHPT), characterized by severely elevated parathyroid hormone levels (PTH), arises from the metabolic abnormalities of end-stage renal disease (ESRD), affecting the majority of patients undergoing dialysis and contributing to risks such as cognitive decline due to PTH's ability to cross the blood–brain barrier and affect brain function (Mathur et al. 2022). SHPT begins early in chronic kidney disease (CKD), typically during stage G2, when impaired phosphate excretion stimulates parathyroid cells to secrete more PTH, even before serum phosphate levels become elevated (Rodzon-Norwicz et al. 2023). As CKD progresses, particularly in stages G4 and G5, hyperphosphatemia and hypocalcemia become more prominent, further stimulating PTH secretion and creating a pathological cycle of glandular hypertrophy and hormonal excess (Habaset al. 2021). Clinically, SHPT leads to chronic kidney disease–mineral and bone disorder (CKD-MBD), marked by bone pain, spontaneous fractures, soft tissue calcification, and muscle weakness (Shah et al. 2024). It also contributes to serious cardiovascular complications, including vascular calcification and hypertrophic cardiomyopathy, which are major contributors to morbidity and mortality in dialysis patients (Galassi et al. 2021; (Rodzon-Norwicz et al. 2023). Without appropriate intervention, these effects significantly reduce quality of life and survival in CKD patients.

Parathyroid hormone (PTH), the main regulator of calcium balance, maintains calcium levels by mobilizing both calcium and inorganic phosphate from bone through osteoclast activation. Though it increases phosphate levels, PTH simultaneously reduces phosphate reabsorption in the renal tubules, increasing phosphaturia to compensate (Rodzon-Norwicz et al 2023). Chronic elevation of PTH in secondary hyperparathyroidism (SHPT) leads to mineral and bone disorders, such as renal osteodystrophy and vascular calcifications, which heighten cardiovascular risk (Stack, 2024). High-turnover bone disease, characterized by increased osteolysis and fibrosis, results from persistently elevated PTH levels (often >800 pg/mL), severely affecting bone integrity (Muppidiet al 2020). CKD-related imbalances in calcium and phosphate further exacerbate chronic kidney disease-mineral bone

disorder (CKD-MBD), which includes pain, fractures, soft tissue calcifications, and increased mortality due to cardiovascular events(Shah et al. 2024; Salera et al. 2025). Additionally, higher iPTH levels correlate with increased uric acid and systemic inflammation in patients with cardiovascular disease (CVD), reinforcing the systemic impact of PTH dysregulation (Checa-Roset al. 2025).

Intravenous doxercalciferol and oral calcitriol are both active vitamin D analogs used to manage secondary hyperparathyroidism (SHPT) in hemodialysis patients, but they differ in pharmacologic properties and clinical application. Oral calcitriol, the active form of vitamin D, binds directly to vitamin D receptors, effectively lowering parathyroid hormone (PTH) levels but often at the cost of increased serum calcium and phosphate levels, leading to higher vascular calcification risk (Thadhani et al., 2020). In contrast, doxercalciferol, a synthetic vitamin D analog, is a prodrug requiring hepatic activation. When administered intravenously, it produces a more stable PTH suppression with fewer calcemic side effects (Yang et al., 2025). A recent randomized trial found that doxercalciferol suppressed PTH by over 40% in 72.5% of patients compared to 58% in the calcitriol group (Yang et al., 2025), with SHPT prevalence reaching 86% in dialysis cohorts (Thadhani et al., 2020). Clinical preference now favors intravenous doxercalciferol in dialysis due to its dosing control and reduced hypercalcemia risk.

Recent clinical trials and meta-analyses have provided comparative insights into the effectiveness of calcitriol and doxercalciferol in managing secondary hyperparathyroidism in hemodialysis patients. A multicenter phase II trial revealed that intravenous doxercalciferol suppressed parathyroid hormone (PTH) levels by over 40% in 72.5% of patients, compared to 58% for oral calcitriol (Yang et al., 2025). Moreover, a recent meta-analysis indicated that doxercalciferol was associated with a significantly lower risk of hypercalcemia compared to calcitriol (Abreu et al., 2021). In practical terms, the prevalence of secondary hyperparathyroidism in hemodialysis patients is approximately 86% (Thadhani et al., 2020). Additionally, evidence suggests that calcitriol effectively reduces PTH but leads to higher serum calcium and phosphate levels, increasing vascular calcification risks, while

doxercalciferol maintains better biochemical balance with fewer adverse events (Magagnoli et al., 2024). These findings emphasize a clinical shift favoring intravenous doxercalciferol for safer and more stable management of PTH levels in this high-risk population.

In countries like Bangladesh and other low-to-middle income regions, the growing burden of chronic kidney disease and dependence on maintenance hemodialysis pose substantial public health challenges. The cost and accessibility of medications become critical factors influencing treatment decisions. While oral calcitriol is widely available and inexpensive, intravenous options like doxercalciferol may be limited to tertiary hospitals or urban dialysis units. Additionally, patient adherence to oral therapy can be inconsistent due to pill burden, gastrointestinal disturbances, and lack of awareness. In such settings, evidence that supports the use of one agent over the other, especially if it demonstrates better biochemical control or fewer side effects, is of immense value. Therefore, evaluating the comparative efficacy and safety of these two agents within a regional context is not only timely but essential for developing cost-effective, practical, and evidence-based SHPT treatment protocols for dialysis patients in resource-constrained environments.

Despite the widespread use of calcitriol and doxercalciferol in dialysis centers, the literature still lacks high-quality, head-to-head comparisons focusing specifically on hemodialysis patients in low-resource environments. Most existing data derive from Western populations, and generalizability to LMICs remains uncertain. Moreover, the impacts of administration routes on patient compliance, PTH suppression, and adverse event profiles are yet to be fully elucidated. Given the rising incidence of CKD in South Asia, a comparative evaluation of intravenous doxercalciferol and oral calcitriol in terms of PTH control, safety outcomes, and patient practicality is highly relevant. This study aims to fill this critical evidence gap and inform clinical decision-making tailored to the realities of resource-constrained settings.

## **2. Rationale**

The route of administration plays a crucial role in determining treatment outcomes in patients with secondary hyperparathyroidism (SHPT) undergoing hemodialysis. Oral calcitriol can be hard to manage due to poor adherence from the high pill burden. In contrast, IV administration of doxercalciferol after hemodialysis provides a practical and patient-friendly alternative, as it eliminates the need for extra cannulation by utilizing the existing vascular access used during dialysis. While previous studies have reported that IV doxercalciferol achieves better outcomes in lowering parathyroid hormone (PTH) levels compared to oral calcitriol, it remains unclear whether these benefits are reproducible in our local patient population. Given the rising prevalence of SHPT and the expansion of hemodialysis services in Bangladesh, it is essential to investigate whether IV doxercalciferol can provide clinical benefits in this setting. Therefore, this study aims to evaluate the comparative effectiveness of IV doxercalciferol versus oral calcitriol in controlling PTH levels among hemodialysis patients, addressing a critical gap in local clinical evidence to inform optimal treatment strategies.

### **3. Research question/Hypothesis:**

**3.1 Research question:** What is the effect of intravenous doxercalciferol compared to oral calcitriol in reducing parathyroid hormone (PTH) levels among patients undergoing hemodialysis?

**3.2 Research hypothesis:** Intravenous doxercalciferol is more effective than oral calcitriol in reducing parathyroid hormone (PTH) levels in patients undergoing hemodialysis.

## **4. Objectives**

**4.1 General objectives:** To compare the effectiveness and safety of intravenous doxercalciferol and oral calcitriol in reducing parathyroid hormone (PTH) levels in patients undergoing hemodialysis.

### **Specific objectives:**

1. To detect and compare the reduction of serum parathyroid hormone (PTH) levels following treatment with intravenous doxercalciferol and oral calcitriol in hemodialysis patients.
2. To assess the changes in serum calcium and phosphate levels associated with each treatment modality.
3. To evaluate the incidence of treatment-related hypercalcemia and hyperphosphatemia in both treatment groups.
4. To compare the adverse events and efficacy profiles of intravenous doxercalciferol and oral calcitriol in the management of secondary hyperparathyroidism in hemodialysis patients.

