**5.7 Exclusion criteria:**

1. Patients with known case of primary hyperparathyroidism or parathyroidectomy.
2. Serum calcium  $>10$  mg/dL or phosphate  $>5.5$  mg/dL at baseline.
3. Active liver disease or significant hepatic dysfunction, Alcoholism.
4. History of hypersensitivity to vitamin D analogs.
5. Pregnant or breastfeeding women.
6. Concurrent use of medications (e.g. bisphosphonates).
7. Patients with active malignancy (e.g. multiple myeloma, bronchogenic carcinoma).

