**5.11 Data collection procedure:**

All ESRD patients on hemodialysis will be consecutively and prospectively screened according to the above inclusion and exclusion criteria to identify eligible participants for randomization. Eligible patients and their legal relatives will then fully explain the study protocol, their role in the study, and the risks of the study. They will be informed of their right to withdraw from the study at any stage. After getting written informed consent, they will be finally enrolled in the study.

- **Baseline evaluation:** Baseline data will be collected at enrollment, including demographic and anthropometric variables such as age, sex, monthly income, height, weight, and body mass index (BMI). These variables will be recorded systematically for both groups to ensure proper group characterization and comparability. In addition, clinical information will be documented, focusing on the presence of comorbidities such as diabetes mellitus (DM) and hypertension (HTN). Baseline serum calcium, serum phosphate, iPTH will be recorded in the case record form. washout period of calcitriol will be conducted prior to randomization.
- **Randomization:** After consenting, eligible individuals will be recruited consecutively and randomly assigned in 1:1 ratio (block size of four), with a computer-generated randomization list, to one of the two treatment arms (Experimental group and Control group). Group 1 (Control Group) Will received oral calcitriol alone with standard treatment of CKD. Group 2 (Experimental Group) will received post-hemodialysis intravenous (IV) doxercalciferol alone with standard treatment of CKD. All participants, regardless of group allocation, who are on calcium acetate or sevelamer will continue these medications at their existing doses throughout the study period.
- **Blinding:** Blinding of the study medication is not possible because of resource limitations. It is an open-label study and both the researcher and the subject know about the drugs they are receiving.

**Sample Collection procedure:** Blood samples will be collected pre-dialysis after an overnight fasting period, with all aseptic precaution 5 mL of venous blood drawn into appropriate vacutainers.

- iPTH will be measured using a chemiluminescence immunoassay (CLIA).
- Serum calcium and phosphate will be analyzed using colorimetric methods on a Beckman Coulter AU480 or equivalent validated clinical chemistry analyzer.

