All laboratory analyses will be conducted in an ISO-certified laboratory, ensuring accuracy and standardization of results.

**Treatment:** The treatment phase will last for twelve weeks. Experimental subjects will receive an intravenous loading dose of doxercalciferol 4 micrograms after dialysis, in addition to their standard routine medications. Each Dose of doxercalciferol will be given after skin sensitivity test. Skin sensitivity test will be performed by a small amount of doxercalciferol inject intradermally → wait 10-15 minutes → see for localized swelling and redness. Though skin sensitivity test negative despite patients may developed anaphylactic reaction, Then following measure will be taken. Prevent further contact with allergen, ensure airway patency, anti histamine, hydrocortisone, nebulize with sulbutamol, adreline, i/v fluids. Patients in the control group will receive oral calcitriol 0.25 micrograms once daily, along with their standard routine medications.

**Evaluation of the patient at 6 Weeks:** The patients will be followed up at 6 weeks ( $\pm 2$  days) and will instructed to report immediately in case of any advance events following consumption of the drug. Tolerability will be assessed using an adverse event profile (adverse events, serious adverse events). Safety population consist of subjects who receive at least one dose of study medication. Body weight and sitting blood pressure will be evaluated. patients will be removed if any of the withdrawals mentioned above are observed, and appropriate management will be initiated in the nephrology department of CMCH.

**Follow –up and outcome assessment:** All the patients will be examined again after 12 weeks ( $\pm 2$  days) The same biochemical parameters—serum calcium, serum phosphate, iPTH,—will be reassessed under the same collection and analysis protocols. These follow-up results will be compared with baseline values to evaluate the relative efficacy of IV doxercalciferol versus oral calcitriol in controlling SHPT and maintaining mineral balance. All data, including demographic, clinical, and laboratory results, will be systematically documented in a Case Record Form (CRF) to ensure completeness and integrity of the dataset.

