#### **5.12. Data analysis:**

Statistical analysis will be performed using Statistical Package for Social Science (SPSS) version 27.0 (IBM Corp., Armonk, NY, USA). Baseline continuous variables such as age, monthly income, height, weight, BMI, blood pressure, duration of hemodialysis, and biochemical markers (serum calcium, phosphate, parathyroid hormone, and serum creatinine) will be expressed as mean  $\pm$  standard deviation (SD) or median with interquartile range (IQR) depending on data distribution, while categorical variables such as sex, presence of diabetes mellitus (DM), hypertension (HTN) use will be presented as frequencies and percentages. Normality of continuous variables will be assessed using the Shapiro-Wilk test. For comparison between the control and experimental groups, independent samples t-test or Mann-Whitney U test will be applied for continuous variables, depending on their distribution, and Chi-square test or Fisher's exact test will be used for categorical variables. Biochemical parameters (serum calcium, phosphate, PTH, and serum creatinine) at baseline and after 12 weeks of follow-up will be compared within each group using paired t-test or Wilcoxon signed-rank test as appropriate. A p-value of less than 0.05 will be considered statistically significant.

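### Within-arm phosphate change and per-arm hyperphosphatemia cannot be credited to the drugs, because a ceiling on the baseline reading is expected to produce a rise in both arms by itself

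*Protocol*

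**What the plan says.** - **Entry rule.** Protocol section 5.7, item 2, excludes calcium above 10 or phosphate above 5.5 "mg/dL at baseline".
- **Baseline.** Section 5.11 states: "Baseline serum calcium, serum phosphate, iPTH will be recorded in the case record form". The case record form has one pre-treatment set of these values and one set at week 12. No separate screening draw or repeat is described.
- **Reference for change.** Section 5.11, on follow-up, states: "These follow-up results will be compared with baseline values to evaluate the relative efficacy of IV doxercalciferol versus oral calcitriol".
- **Analysis.** Under section 5.12 the biochemical values at baseline and week 12 "will be compared within each group using paired t-test or Wilcoxon signed-rank test as appropriate". The same section also plans tests between arms: "For comparison between the control and experimental groups, independent samples t-test or Mann-Whitney U test will be applied for continuous variables", with chi-square or Fisher's exact tests for categorical variables.
- **Objectives.** Specific objective 2 looks for calcium and phosphate changes linked to each treatment. Objective 3 is "To evaluate the incidence of treatment-related hypercalcemia and hyperphosphatemia in both treatment groups".
- **Arms.** Both arms receive an active vitamin D compound; no arm is untreated. The protocol gives no numerical definition of hypercalcemia or hyperphosphatemia as an outcome.

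**The concern.** If patients enter only when a fluctuating measurement is below a limit, some are admitted because that reading happened to be low for them. Their next reading is higher on average even if nothing has changed. This is regression to the mean. A paired test against the qualifying reading counts the shift as a treatment effect. Since nobody starts above 5.5, every later value above it also looks like a new event.

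The introduction says that in advanced disease "hyperphosphatemia and hypocalcemia become more prominent, further stimulating PTH secretion". This suggests that the phosphate ceiling cuts into the body of the distribution and not only its far tail.

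With no untreated arm, nothing inside either arm separates this shift from a drug effect. The plan could therefore report a significant phosphate rise, and a sizeable rate of hyperphosphatemia described as treatment-related, for two drugs that leave phosphate unchanged. A second risk is that one arm's paired test crosses 0.05 and the other's does not, and a reader takes that as a difference between the drugs.

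**Working it through.** The protocol gives no mean, SD or repeat-measure correlation for phosphate or calcium, and no expected change. There is no figure of its own to reproduce on this point.

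**From the protocol:** ceilings c = 5.5 (phosphate) and c = 10 (calcium), section 5.7; n = 43 per arm before the dropout allowance, section 5.8; follow-up at 12 weeks.

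**Assumed:** in screened patients the true phosphate is normal with mean μ = 4.5 to 5.5 and between-patient SD 1.0 to 1.2. Each reading adds independent within-patient variation with SD 0.7 to 1.0. There is no drug effect, and the same draw serves eligibility and baseline.

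**Formulas.** Let S² = SDb² + SDw², ρ = SDb²/S², a = (c − μ)/S and λ = φ(a)/Φ(a).
- Expected rise = (1 − ρ)·S·λ
- Share above c at week 12 = 1 − Φ₂(a, a; ρ)/Φ(a), where Φ₂ is the bivariate normal distribution function
- Variance of change = (1 − ρ)²·S²·(1 − aλ − λ²) + S²·(1 − ρ²)
- Rejection by the paired t-test: noncentral t with 42 df and noncentrality rise/SD(change)·√43, two-sided 5%

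**Worked case** (μ = 5.0, SDb = 1.0, SDw = 0.7):
- S = √1.49 = 1.221; ρ = 1/1.49 = 0.671; a = 0.5/1.221 = 0.410; λ = 0.3668/0.6590 = 0.557.
- Rise = 0.329 × 1.221 × 0.557 = 0.22 mg/dL.
- Share above 5.5 = 18%.
- SD of change = 0.945; noncentrality = 0.2235/0.945 × 6.557 = 1.55; rejection = 33%.

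**Phosphate over the assumed SD ranges:**

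| Screened mean | Expected rise (mg/dL) | Above 5.5 at week 12 | Paired test significant |
|---|---|---|---|
| 4.5 | 0.14-0.29 | 12-17% | 16-29% |
| 5.0 | 0.21-0.42 | 17-24% | 28-53% |
| 5.5 | 0.28-0.56 | 23-33% | 48-80% |

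Nearly all of these rejections are in the upward direction.

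**Wider assumptions** (mean 4.5-6.0, total SD 1.2-1.8, correlation 0.4-0.8; 36 combinations): the expected rise is positive in every one, from 0.09 to 1.06 mg/dL. Between 9% and 49% exceed 5.5, and the paired test is significant upward in 10% to 99% of trials.

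**Calcium** (assumed mean 8.8-9.2, SDb 0.6, SDw 0.4-0.5): rise 0.02-0.09 mg/dL, 3-10% above 10, paired-test rejection 6-13%.

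**Between arms.** I simulated 10,000 trials with 43 per arm and no drug effect, at (μ, SDb, SDw) = (5.0, 1.0, 0.7) and (5.5, 1.0, 1.0). The independent t-test rejected in 5.3% and 5.4% for change, and in 5.2% and 5.0% for the week-12 value. The shift is the same in both arms and cancels.

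**The case against.** **The trial's inference is comparative.** The hypothesis, the general objective and the planned t, Mann-Whitney, chi-square and Fisher tests all set one arm against the other. This stands. A reader might infer that the comparison of the two drugs is biased. It is not, since randomisation gives both arms the same expected shift. The paired tests also bear on objective 2 only; they cannot yield the incidence in objective 3.

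**The single draw is inferred.** Section 5.11 places screening before consent and baseline data at enrolment, so two draws are possible. This stands in part. Section 5.7 nevertheless applies the ceiling to the baseline value, and the case record form holds only one pre-treatment set, so one truncated reading is the natural interpretation. The protocol does not say whether it is drawn before or after the calcitriol washout.

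**The 5.5 threshold is borrowed.** The protocol never says that a week-12 value above 5.5 will be called treatment-related, and the safety-monitoring form has a column for relation to the intervention. This stands: the 12-33% depends on using the entry limit as the outcome threshold. That no single-arm count can establish causation does not depend on it.

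**The size rests on assumptions.** This stands. A rise is expected on average but is not certain in a given arm.

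**Descriptive status could be left to an analysis plan.** This is fair for that one sentence. The wording of the objectives and the use of paired tests are, however, fixed in the protocol.

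**Conclusion.** The concern holds for within-arm interpretation, chiefly of phosphate. As written, the paired tests cannot show change due to each treatment (objective 2), and an incidence within one arm cannot be called treatment-related (objective 3).

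With no drug effect, and if one reading serves both purposes, the expected phosphate rise is about 0.14-0.56 mg/dL. The paired test is then significant in about 16-80% of trials. The direction needs only a ceiling on the baseline value, a stable population and a correlation below 1; the size depends on the assumed mean and SDs.

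The documents do not support three stronger readings:
- **The between-arm results are invalid.** They are not.
- **Calcium is affected to a similar degree.** Its shift is small unless the screened mean lies close to 10.
- **The entry rule on iPTH creates a matching spurious fall from one sample.** Section 5.9 speaks of sustained or chronic elevation above 300 pg/mL, which is not a single-draw rule.

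This is a worthwhile correction at almost no cost, not a flaw in the randomised comparison.

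**What to change.** 1. **Objective 2:** answer it by the between-arm difference in week-12 calcium and phosphate, preferably adjusted for baseline.
2. **Objective 3:** reword it to compare between arms the proportions with calcium or phosphate above stated limits at week 12, and drop the treatment-related qualifier. State the limits. If the values in section 5.7 are used, no enrolled patient starts above them, so week-12 exceedances are new ones.
3. **Section 5.12:** add that within-group paired tests of calcium and phosphate are descriptive and are not evidence of a drug effect.

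The eligibility limits and the way they are applied stay as they are. Applying the ceiling to an older result would change an entry rule. It would also let patients already above the limit count as new cases at week 12. The cost is a few sentences and one adjusted comparison from data already being collected. No extra visit, sample or patient is needed.

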**Operational definitions:**

**Parathyroid Hormone (PTH):** Parathyroid Hormone (PTH) will be measured as intact PTH (iPTH) in picograms per milliliter (pg/mL) using a second-generation immunoassay. In accordance with KDIGO recommendations, for patients receiving maintenance hemodialysis, iPTH levels sustained above 300 pg/mL are considered indicative of secondary hyperparathyroidism (SHPT).

**Doxercalciferol:** Doxercalciferol will be administered intravenously post-hemodialysis in doses ranging from 1–4 micrograms per session. Its use will follow KDIGO recommendations for selective vitamin D receptor activator (VDRA) therapy to suppress iPTH levels while minimizing the risk of hypercalcemia and hyperphosphatemia in dialysis patients.

**Calcitriol:** Calcitriol will be administered orally on a daily or alternate-day schedule, titrated based on iPTH, calcium, and phosphate levels.

**Maintenance Hemodialysis:** Maintenance hemodialysis is defined as a twice-weekly dialysis regimen maintained for a minimum duration of three months in patients with end-stage kidney disease, consistent with KDIGO standards for long-term renal replacement therapy.

**Secondary Hyperparathyroidism (SHPT):** Secondary hyperparathyroidism (SHPT) is defined as a chronic elevation of iPTH above 300 pg/mL in patients undergoing maintenance hemodialysis, with supporting evidence of disrupted calcium, phosphate, and vitamin D metabolism as outlined in KDIGO guidelines for CKD-MBD.

**Adverse Events:** An AE is defined as any untoward medical occurrence in a clinical trial patient during the study, the event does not necessarily have a causal relationship with that treatment. Therefore, an AE can be any unfavorable and unintended sign (including any clinically significant abnormal laboratory finding), symptoms, or disease, temporally associated with using a medicinal product.

**Major adverse events:** Will defined as any event leading to admission or prolonged admission, anaphylactic reactions, withdrawal, or death.

**Minor adverse events:** Will defined as minor if it does not require admission to the hospital or withdrawal of the drug. Such as nausea, vomiting, edema, headache, fatigue, metallic test, loss of appetite, constipation.

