#### Adverse events (AE) Patient ID

Patient ID	AE Onset	AE End	Severity	Related to intervention	Action taken	Outcome	Comment
1							
2							
3							
4							

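### Objective 3 counts only treatment-related hypercalcemia and hyperphosphatemia in an open-label trial; the qualifier adds an avoidable judgement to a laboratory outcome and should go

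*Protocol*

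**What the plan says.** In the protocol's list of specific objectives, item 3 reads "To evaluate the incidence of treatment-related hypercalcemia and hyperphosphatemia in both treatment groups". Items 2 and 4, on changes in calcium and phosphate and on adverse events, carry no causal qualifier.

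The other relevant places are these:

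- **Operational definitions, Adverse Events.** Abnormal laboratory findings of clinical significance are included, and "the event does not necessarily have a causal relationship with that treatment".
- **Section 5.11, Blinding.** "It is an open-label study and both the researcher and the subject know about the drugs they are receiving".
- **Section 5.11, Randomization.** Participants in either group "who are on calcium acetate or sevelamer will continue these medications at their existing doses throughout the study period".
- **Section 5.11, Follow-up and outcome assessment.** At 12 weeks calcium, phosphate and iPTH "will be reassessed under the same collection and analysis protocols".
- **Case record form.** It has numeric fields for calcium and phosphate at baseline and 12 weeks, and no relatedness item.
- **Data and Safety Monitoring Plan.** The blank adverse-event table has a column headed "Related to intervention".
- **Section 5.7.** Patients with calcium above 10 or phosphate above 5.5 "mg/dL at baseline" are excluded.

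**The concern.** Serum calcium and phosphate come from an analyser, so knowledge of the allocation has little room to influence them. Objective 3, read as written, gives some of that protection away. A value above the limit counts only if somebody decides that the study drug caused it. The protocol does not say how that is decided, by whom, or without sight of the allocation.

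Two features make such a judgement vulnerable. The introduction already states an expectation that calcitriol raises calcium and phosphate more than doxercalciferol does. Binders, one of them calcium-based, continue in both arms and offer another explanation for a high or low threshold of suspicion in any given patient. If the explanation chosen depends even partly on the arm, identical laboratory results can give different incidences.

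The judgement also buys nothing. Randomization already supplies the causal comparison: a difference between arms in all exceedances estimates the effect of assignment without attributing any single event.

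At stake is one secondary safety comparison, not the PTH result.

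**Working it through.** **Step 1: can the literal reading be carried out?** A count of treatment-related events needs three things: a limit, a causality rule, and someone to apply the rule.

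- *Limit.* The only calcium and phosphate thresholds in the protocol are the exclusion limits in section 5.7, and they are not stated as event definitions. A statistical analysis plan could supply a limit, so its absence is not counted as a fault here.
- *Causality rule and assessor.* Neither is given. The relatedness column in the monitoring table is the only trace of a causality decision, and nothing links it to objective 3.
- *Blinding of the decision.* Not provided; by section 5.11 "both the researcher and the subject know about the drugs they are receiving".

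**Step 2: can the outcome be counted without attribution?** Yes. The numeric 12-week values are collected in both arms under the same procedures. Everyone must start at or below 10 mg/dL for calcium and 5.5 mg/dL for phosphate, so a value above those limits at 12 weeks is new since baseline.

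**Step 3: how much could attribution matter?** The protocol states no rate or power for either event, so there is no figure to reproduce. What follows is illustration.

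Inputs from the protocol: 43 per arm before and 49 per arm after the dropout allowance, as printed in section 5.8; chi-square or Fisher's exact test at 0.05 (section 5.12).

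Assumed inputs: a true event rate p, equal in both arms; a share of events called related, r_C on calcitriol and r_D on doxercalciferol.

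The counted events are then binomial with probabilities p × r_C and p × r_D. The chance of a significant result is the sum, over all pairs of counts (a, b), of Bin(a; n, p·r_C) × Bin(b; n, p·r_D) for those pairs with a test p-value below 0.05.

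Worked case with n = 43, p = 0.20, r_C = 0.9, r_D = 0.5:

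- True expected events per arm: 43 × 0.20 = 8.6.
- Counted on calcitriol: 8.6 × 0.9 = 7.7 (18%).
- Counted on doxercalciferol: 8.6 × 0.5 = 4.3 (10%).

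| Attribution (calcitriol v doxercalciferol) | Chi-square, p<0.05 | Fisher, p<0.05 |
|---|---|---|
| All events counted | 5.3% | 2.6% |
| 90% v 70% | 8.4% | 4.3% |
| 90% v 50% | 19.6% | 11.6% |

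In the last row almost all significant results favor doxercalciferol (19.4 of the 19.6 percentage points by chi-square).

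Ranges over true rates of 10% to 40% and 43 to 49 per arm:

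| Attribution | Chi-square | Fisher |
|---|---|---|
| All events counted | 4.9–5.9% | 1.7–3.1% |
| 90% v 70% | 7–13% | 2–9% |
| 90% v 50% | 12–42% | 3–34% |

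Counting every exceedance keeps the error rate near or below nominal. Differential attribution raises it by an amount that depends wholly on the assumed shares.

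**The case against.** The strongest reply is that the protocol describes no attribution step for laboratory values. The case record form holds only numbers, section 5.11 says that follow-up values will be set against baseline, section 5.12 names no attributed endpoint, and the relatedness column belongs to an unfilled monitoring template. On this view the adjective is loose wording for treatment-emergent. That reading is quite possible and cannot be excluded. It does not remove the point: the protocol never says so, and an analysis plan that counted all events would depart from objective 3 as worded. If treatment-emergent was meant, the same edit settles it.

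It can also be said that unfiltered comparisons are already planned. This stands, and it limits the damage. Objective 2 compares calcium and phosphate changes, and objective 4 compares adverse events under a definition that does not require causality. A spurious difference under objective 3 would sit beside those results. A general adverse-event definition alongside a narrower objective is a difference in scope, not a contradiction.

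Third, the attribution shares are invented. That is right. Nor need the effect be significant: with 10 of 49 true events per arm and attribution of 80% against 40%, the counts are 8/49 and 4/49, a twofold ratio with Fisher p = 0.36.

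**Conclusion.** The point holds as a matter of wording and avoidable risk. Objective 3 restricts a laboratory incidence to events judged drug-related, in an open-label trial, with no attribution rule or blinded assessor. Taken literally, that could bias this one comparison. Its size cannot be estimated from the protocol; the percentages above rest on assumed event rates and attribution shares and show only that a false difference can arise.

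A reader might infer more, and the protocol does not support it:

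- That an unblinded investigator will adjudicate laboratory results. This is an inference from the objective, the open-label statement and the template column; no text assigns the task.
- That this is the trial's main safety endpoint. The protocol does not rank its safety outcomes.
- That the bias favors the stated hypothesis. The hypothesis in section 3.2 concerns PTH only; the expectation of fewer calcemic effects is background in the introduction.
- That the safety comparison as a whole is compromised. Objectives 2 and 4 are untouched by the qualifier.

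**What to change.** Delete the qualifier treatment-related from objective 3. Define the outcome as the number of participants whose scheduled 12-week calcium (and, separately, phosphate) exceeds one prespecified analysis limit, applied identically in both arms and compared by randomized arm whatever the suspected cause. The baseline exclusion limits of 10 and 5.5 mg/dL are one available choice. They would serve as an analysis cut-off only, not as a rule for managing patients. Report any relatedness judgement descriptively, outside the comparison.

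The cost is a wording change in objective 3 and a sentence in section 5.12 giving the limit and the test. No new data are needed, since the 12-week values are already collected. The drawback is that counts in both arms will include some events unrelated to study drug, and some participants who started just under the limit and crossed it through ordinary variation. Because one rule applies to both arms, neither should favor an arm systematically, though both may dilute a real difference.
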